**Each of the following volumes and normal structures must be delineated on each slice of the planning CT:**

Post Lumpectomy Volumes: Ipsilateral and Contralateral Breast and Lumpectomy Cavity.

Normal tissue: Right and left lung, contralateral breast, heart, thyroid.

Normal tissues should be delineated as follows:

Breast: Breast CTV. Includes the palpable breast tissue demarcated with radio-opaque markers at CT simulation, the apparent CT glandular breast tissue visualized by CT, consensus definitions of anatomical borders, and the Lumpectomy CTV from the RTOG breast cancer atlas. The breast CTV is limited anteriorly within 5 mm from the skin and posteriorly to the anterior surface of the pectoralis, serratus anterior muscle excluding

chest wall, boney thorax and lung. In general, the pectoralis and/or serratus anterior muscles are excluded from the breast CTV unless clinically warranted by the patient's pathology. The breast CT should generally follow consensus guidelines

**Contralateral breast:** Includes the apparent CT glandular breast tissue visualized by CT and consensus definitions of anatomical borders from the RTOG Breast Atlas.

In general the borders are:

- *Posterior border:* At the anterior surface of the pectoralis, serratus anterior muscles excluding Breast, ribs, boney thorax, and lung/heart.
- *Medial border:* The sternal-costal junction.
- *Lateral border:* Varies based on the size of the breast, but typically is at the mid-axillary line and excludes the ipsilateral latissimus dorsi muscle.
- *Cephalad border:* Should be similar to that of the ipsilateral breast CTV.
- *Anterior border:* Skin minus 5 mm to minimize inaccuracy of dose calculation at the skin surface.

**Ipsilateral and contralateral lung:** These may be contoured with auto-segmentation with manual verification.

**Heart:** This is to be contoured on all cases – not just the left sided cases. The heart should be contoured beginning just inferior to the level in which the pulmonary trunk branches into the left and right pulmonary arteries (pa). Above the pa, none of the heart's 4 chambers are present. The heart should be contoured on every contiguous slice thereafter to its inferior most extent near the diaphragm. The following structures, if identifiable, should be excluded from the heart contour: esophagus, great vessels (ascending and descending aorta, inferior vena cava). One need not include pericardial fat, if present. Contouring along the pericardium itself, when visible, is appropriate.

**Thyroid:** The thyroid is easily visible on a non-contrast CT due to its preferential absorption of iodine, rendering it "brighter" or denser than the surrounding neck soft tissues. The left and right lobes of the thyroid are somewhat triangular in shape and often do not converge anteriorly at mid-line. All "bright" thyroid tissue should be contoured. For patients who have undergone total thyroidectomy, there may be no thyroid tissue to contour.

## IMRT

The following definitions and conditions are applied concerning IMRT in this protocol:

- 1) The treatment plan will be considered IMRT for the purposes of this protocol if an inverse planned optimization is used to determine the beam weights to meet the target and critical structure dose-volume constraints.
- 2) A plan generated by direct aperture optimization that employs an inverse planning algorithm is considered as IMRT when the target and critical structure dose-volume constraints are met and at least 3 apertures for each beam direction are used.

Protocol name: NOVEMBER (Novem- (9), BrEast Radiation), A Phase II trial of a 9 day course of whole breast radiotherapy for early stage breast cancer.

Version Date: 23NOV2021

Principal Investigator: [name]

3) If IMRT is combined with the standard open medial and lateral tangential fields for whole breast irradiation, the IMRT beam, as described in number 1) above, should deliver > 50% of the total number of monitor units for the beam orientation.

4) If an IMRT plan is used with another IMRT plan, forward-planning photon beams, and/or electron beam, the composite dose distribution and DVHs should be generated.

5) All standard IMRT planning and delivery systems using MLC (step-and-shoot, dynamic MLC, slide-and shoot, VMAT, tomotherapy) are allowed and classified as IMRT as long as target and critical structure dose-volume constraints are met.

6) IMRT planning and delivery systems using physical beam-intensity compensators designed by an inverse algorithm to modulate beam intensity so that the required dose constraints are met are also accepted as IMRT.

All plans that are not fit into the above definitions and conditions are classified as 3DCRT plans. Specifically:

- The plans generated using forward-planning methods or segmental techniques such as “field-in-field” to meet dose-volume constraints are considered as 3DCRT plans. These forward-planned or segmental treatment techniques are those intended mainly to improve the uniformity of the dose distribution, but not to produce steep dose gradients to protect critical structures (e.g. heart or lung).
- The plans with the number of apertures < 3 for each beam direction are considered 3DCRT plans even if they were generated with inverse planning algorithms.

### 5.3.2 Treatment Planning

The goals of treatment planning in this study in both arms are to encompass the breast and minimize inclusion of the heart and lung.

Field arrangements for 3D conformal and IMRT of the breast are defined below with some discretion of the treating physician. Multiple beam arrangements are to be designed during the treatment planning process to produce an optimal plan that meets the dose-volume constraints on the target volumes and normal tissues outlined below. This trial is specifically evaluating toxicity and cosmesis; therefore we have set tight constraints on maximum doses.

Treatment plans must meet Dose Volume Constraints for the contoured targets and normal structures. Various treatment approaches may be used to develop treatment plans.

Ipsilateral Breast CTV to PTV expansion is a range of 5-7mm, based on practice and technical capabilities.

#### **The following volumes are to be delineated:**

**Lumpectomy GTV:** Contour using all available clinical and radiographic information including the excision cavity volume, architectural distortion, lumpectomy scar, seroma and/or extent of surgical clips (clips are strongly recommended). Patients without a clearly identifiable lumpectomy bed are not eligible for protocol participation.

Protocol name: NOVEMBER (Novem- (9), BrEast Radiation), A Phase II trial of a 9 day course of whole breast radiotherapy for early stage breast cancer.

Version Date: 23NOV2021

Principal Investigator: [name]

**Lumpectomy CTV:** Lumpectomy GTV + 1 cm 3D expansion. Limit the CTV posteriorly at anterior surface of the pectoralis major and anterolaterally 5 mm from skin and should not cross midline. In general, the pectoralis and/or serratus anterior muscles are excluded from the lumpectomy CTV unless clinically warranted by the patient's pathology. The Lumpectomy CTV should not extend outside of the Breast CTV and should be trimmed if necessary to accomplish this.

**Lumpectomy PTV:** Lumpectomy CTV + 5 mm 3D expansion (excludes heart).

**Lumpectomy PTV Eval:** Since a substantial part of the Lumpectomy PTV often extends outside the patient (especially for superficial cavities), the Lumpectomy PTV is then copied to a Lumpectomy PTV Eval which is edited. This Lumpectomy PTV EvaL is limited to exclude the part outside the ipsilateral breast and the first 5 mm of tissue under the skin (in order to remove most of the build up region for the DVH analysis) and excluding the Lumpectomy PTV expansion beyond the posterior extent of breast tissue (Breast, pectoralis muscles and lung) when pertinent. The lumpectomy PTV should not cross midline. This Lumpectomy PTV Eval is the structure used for DVH constraints and analysis. This Lumpectomy PTV Eval cannot be used for beam aperture generation.

**Breast CTV:** Includes the palpable breast tissue demarcated with radio-opaque markers at CT simulation (see section 5.3.1), the apparent CT glandular breast tissue visualized by CT, consensus definitions of anatomical borders, and the Lumpectomy CTV from the breast cancer atlas (section 5.3.1). The breast CTV is limited anteriorly within 5 mm from the skin and posteriorly to the anterior surface of the pectoralis, serratus anterior muscle excluding chest wall, boney thorax and lung. In general, the pectoralis and/or serratus anterior muscles are excluded from the breast CTV unless clinically warranted by the patient's pathology. The breast CT should generally follow consensus guidelines

**Breast PTV:** Breast CTV + 5-7 mm 3D expansion (exclude heart and do not cross midline).

**Breast PTV Eval:** As a part of the Breast PTV often extends outside the patient, the Breast PTV is then copied to a Breast PTV Eval, which is edited. This Breast PTV Eval is limited anteriorly to exclude the part outside the patient and the first 5 mm of tissue under the skin (in order to remove most of the buildup region for the DVH analysis) and posteriorly is limited to no deeper than the posterior rib surface and excludes lung and heart. This Breast PTV Eval is the structure used for DVH constraints and analysis and not for beam aperture generation.

**Ribs:** The ribs within the Breast PTV need to be contoured as a structure.

### 5.3.3 Dose-Volume Histogram (DVH) Analysis.

#### Breast:

\*\* These are calculated by evaluating the whole breast plan before the summation of the lumpectomy cavity boost.

*Preferred:*  $\geq 95\%$  of the Breast PTV Eval contour that falls within the tangential treatment fields will receive 32.5Gy, 95% of the Breast prescribed dose of 34.2Gy. *Acceptable:*  $\geq 90\%$  of the Breast PTV Eval contour that falls within the tangential treatment fields will receive  $> 30.8\text{Gy}$  which is  $\geq 90\%$  of the whole breast prescribed dose of 34.2 Gy.

*Maximum Dose to Breast:* Less than 10cc of PTV Eval will receive  $> 107\%$  dose or 36.6 Gy for a prescribed breast/Breast dose of 34.2 Gy. Less than 0.03cc can receive  $> 115\%$  of dose, 39.3Gy.

\*\* These are calculated by evaluating the entire plan sum, inclusive of the lumpectomy cavity integrated boost.

*Preferred:*  $\leq 30\%$  of the breast PTV Eval will receive  $> 100\%$  of the boost prescribed dose of 39.6Gy. *Acceptable*  $\leq 35\%$  of the breast PTV Eval will receive  $> 100\%$  of the boost prescribed dose of 39.6Gy.

*Preferred:*  $\leq 50\%$  of the breast PTV Eval will receive  $> 37\text{Gy}$ . *Acceptable:*  $\leq 50\%$  of the breast PTV Eval will receive  $> 38.3\text{Gy}$ .

### **Lumpectomy:**

\*\* These are calculated by evaluating the entire plan sum, inclusive of the lumpectomy cavity integrated boost.

*Preferred:*  $\geq 95\%$  of the Lumpectomy PTV Eval contour will receive 37.6Gy, 95% of the Lumpectomy prescribed dose of 39.6Gy. *Acceptable:*  $\geq 90\%$  of the Lumpectomy or Lumpectomy PTV Eval contour that falls within the tangential treatment fields will receive  $> 35.6\text{Gy}$  which is  $\geq 90\%$  of the whole Lumpectomy prescribed dose of 39.6 Gy.

*Preferred:*  $\leq 5\%$  of the Lumpectomy PTV Eval will receive  $> 43.5\text{Gy}$ , 110% of the boost prescribed dose of 39.6Gy. *Acceptable*  $\leq 10\%$  of the Lumpectomy PTV Eval will receive  $> 43.5\text{Gy}$

*Preferred:* Maximal dose to greater than 0.03 cc will be 45.5 Gy. *Acceptable* is maximal dose no greater than 47.5 Gy.

### **Contralateral Breast:**

*Preferred:* Less than 10% of the contralateral Breast or breast receives  $> 2\text{ Gy}$ .

*Acceptable:* Less than 10% of the contralateral Breast or breast receives 4 Gy or more.

### **Ipsilateral Lung:**

*Preferred:*  $\leq 35\%$  of the ipsilateral lung should receive  $\geq 14.5\text{ Gy}$ .

*Acceptable:*  $\leq 40\%$  of the ipsilateral lung should receive  $\geq 14.5\text{ Gy}$ .

### **Contralateral Lung:**

*Preferred:*  $\leq 10\%$  of the contralateral lung should receive 4 Gy or more.

*Acceptable* is  $\leq 15\%$  of the contralateral lung should receive 4 Gy or more.

### **Heart:**

*Preferred*  $\leq$  10% of the whole heart should receive  $\geq$  18 Gy for left-sided breast cancers, and  $<$  2% of the heart should receive  $\geq$  18 Gy for right-sided breast cancers.

*Acceptable*:  $\leq$  10% of the whole heart should receive  $\geq$  22 Gy for left-sided breast cancers, and  $<$  2% of the heart should receive  $\geq$  22 Gy for right-sided breast cancers.

*Preferred*: Mean heart dose should be  $\leq$  1.5 Gy.

*Acceptable* is a mean heart dose  $\leq$  2.5 Gy.

Every attempt should be made to make the cardiac exposure to radiation as low as possible.

### **Ribs:**

The max rib dose for the entire plan sum is 36Gy. Blocking the ribs from the boost field will likely be necessary. If the lump PTV\_eval cannot be adequately covered by a minimum dose (90% volume to 90% dose), consider taking the patient off protocol.

#### **5.4 Prohibited Concomitant Medications**

No potential radio-sensitizers may be used concurrent with radiation therapy.

#### **5.5 Duration of Therapy**

Subjects must be withdrawn from the study treatment for the following reasons:

- Subject withdraws consent from the study treatment and/or study procedures. A subject must be removed from the trial at his/her own request or at the request of his/her legally acceptable representative. At any time during the trial and without giving reasons, a subject may decline to participate further. The subject will not suffer any disadvantage as a result.
- Subject is lost to follow-up.
- The development of a second cancer or recurrent disease.
- Death.

Subjects may be withdrawn from the study for the following reasons:

- The subject is non-compliant with radiation treatments, trial procedures, or both; including the use of anti-cancer therapy not prescribed by the study protocol.
- If, in the investigator's opinion, continuation of the trial would be harmful to the subject's well-being.
- Development of an intercurrent illness or situation which would, in the judgment of the investigator, significantly affect assessments of clinical status and trial endpoints.
- Deterioration of ECOG performance status to 4.

Protocol name: NOVEMBER (Novem- (9), BrEast Radiation), A Phase II trial of a 9 day course of whole breast radiotherapy for early stage breast cancer.

Version Date: 23NOV2021

Principal Investigator: [name]

## **6 TOXICITIES AND DOSEAGE MODIFICATION**

This study will utilize the CTCAE (NCI Common Terminology Criteria for Adverse Events) Version 4.0 for adverse event and serious adverse event reporting. Dose Modifications

Radiation doses should not be modified and compliance with the protocol will be determined as defined above, by the ideal and acceptable dose constraint criteria. Dose deviations outside of the acceptable range will be considered major protocol violations. Patients may occasionally require treatment breaks, which should be kept to a minimum. Treatment breaks of up to 2 days will be considered acceptable. Treatment breaks of greater than 2 days are strongly discouraged.

### **6.1 Supportive Care**

All supportive measures consistent with optimal patient care will be given throughout the study.

## 7 STUDY CALENDAR

Laboratory and clinical parameters during treatment are to be followed using individual institutional guidelines and the best clinical judgment of the responsible physician. It is expected that patients on this study will be cared for by physicians experienced in the treatment and supportive care of patients on this trial.

Tests & Observations	Prior to Registration	Before RT	Weekly during RT	2 to 8 weeks post RT	6 months post RT*	12 months post RT*	2 years post RT*	3 years post RT**	5 years Post RT**
Obtain Informed Consent 	X								
H&P	X 								
Symptom Directed Physical 			X	X	X	X	X	X	
ECOG Performance Score	X		X	X	X	X	X	X	
Recurrence Assessment 					X	X	X	X	X 
Adverse Events Assessment 			X	X	X	X	X	X	X 
Photographic Cosmetic Assessment 		X					X		
Serum or Urine HCG	X 								
Breast-Q Survey 		X			X		X		
Health Care Expense Diary			X 						
Health Care Expense Survey				X 					
EQ-5D Survey 		X		X					

\* +/- 6 weeks

\*\* +/- 3 months

1. Assessment of side effects related to radiation therapy should be assessed according to the history and physical examination.
2. For women of childbearing potential. Must be done within 7 days prior to registration.
3. All screening procedures should be performed within 28 days prior to registration except as otherwise noted.
4. Health Care Expense Diary should be provided to the patient each week during RT to assist in recall for the Health Care Expense Survey after radiation completion. (Appendix III)
5. Post hoc chart review only for 5 years.
6. Photographic assessment collection will be done as described in section 8.1.
7. Breast Q Survey should be completed by the patient prior to radiation therapy and at 6 months post radiation therapy. (Appendix I)
8. Health Care Expense Survey should be completed using the Health Care Expense Diary worksheet (Appendix III) during the 2-8 week window and is found in Appendix II.
9. EQ-5D Survey should be completed by the patient prior to radiation therapy and during the post radiation therapy 2-8 week window. (Appendix IV)
10. Disease recurrence will be determined by standard of care assessments as described in section 8.3.
11. Clinical assessments above are a minimum for trial purposes only and do not represent the entirety of necessary medical care. Weekly treatment visits occur once every 5 treatment fractions during radiation. Follow up visits should be scheduled per standard of care and physician discretion. Per NCCN guidelines, clinical follow up visit should occur 1-4 times per year with continued annual mammograms.
12. Identified patients who voluntarily agree to complete the Health Care Expense Survey should be provided this survey at 2-8 weeks post standard of care hypofractionated radiation. (See section 8.4 Economic Analysis for further instruction)
13. Patients who volunteer to complete the Health Care Expense Survey must be provided with the Informed Consent Letter prior to completing the questionnaire.

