## 2.6 Cost Effectiveness

We hypothesize that a 9 fraction course will be more cost effective. Costs will be compared to 45 de-identified patients that were treated with a standard hypofractionated regimen of 19 treatments. Direct costs of medical care to each patient will be estimated using utilization information from HCI financial/claims data. Generalized linear models will then be used to model these costs as a function of treatment, time on study, and all available baseline patient characteristics to assess the extent to which estimated direct cost is impacted by the type of radiation dosing. Given the well-known fact that healthcare costs are typically highly skewed, regression models will employ the appropriate distribution and transformation link.

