## 8.4 Economic Analysis

A reduction in number of radiation treatments and thereby number of visits to the radiation therapy department will benefit patients directly, both in terms of reduced direct and indirect healthcare costs. Direct healthcare costs are expected to go down because of an expected reduction in health care utilizations services (e.g., office visits, emergency room visits, inpatient admissions). With short-course treatment patients may be able to take less time off from work and/or return to work faster. Potential improvements in cosmetic-outcomes and side effects of radiation therapy with short-course therapy could also translate into a reduction in utilization of health care services, further enhancing the economic impact of hypofractionation. Indirect costs are also expected to be lower for the intervention arm because patients in this arm are expected to resume normal activities sooner. This in turn would help save family caregiver time as well as the cost of dependent care, which will further add to the saving in indirect costs. Therefore, robust measurement of the patient resources used to receive radiation therapy and utilization of health services is a critical component of this trial.

Patients will be given a diary with question domains to be filled out weekly during radiation therapy in order to help improve recall (Appendix II, III and IV).

We will utilize available CPT code charges generated from the time of registration to 2-8 weeks after the completion of radiation therapy. We will utilize the HCI financial data to estimate reimbursable charges.

Questions are adapted from the Medical Expenditure Panel Survey-Household Component (MEPS-HC) created by

AHRQ ([https://meps.ahrq.gov/survey\\_comp/hc\\_survey/2014/DD111214.pdf](https://meps.ahrq.gov/survey_comp/hc_survey/2014/DD111214.pdf)).

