For comparison assessment, this survey will be administered to an additional 45 patients undergoing standard of care hypofractionated radiation who are otherwise not eligible or interested in enrollment on this protocol. The Health Care Expense Survey should be provided to the patient and completed by the patient 2-8 weeks post standard of care hypofractionated radiation. The comparison group will either receive a \$20 meal card or be reimbursed for a meal up to \$20, with provision of a receipt from the date of the study visit, after completion of the Health Care Expense Survey. This comparison cohort will be case-matched for distance to treatment facility and employment status.

Collected 2-8 weeks after the completion of radiation:

- Work status prior to breast cancer diagnosis (job for pay or business owner, not including work around the house; including work in a family farm or business even if unpaid).

Protocol name: NOVEMBER (Novem- (9), BrEast Radiation), A Phase II trial of a 9 day course of whole breast radiotherapy for early stage breast cancer.

Version Date: 23NOV2021

Principal Investigator: [name]

- If working number of days working per week.
- If working, number of hours working per day.
- Profession and the job title.
- Total number of hours spent for each radiation treatment (time from leaving home or work to return to home or work).
- Distance from radiation treatment facility from home or work.
- Means of getting to radiation treatment facility (ask if only one modality used or a combination, if a combination record number of days for each modality).

1) Car

- Approximate cost for parking
- Did patient drive, was patient driven, or a combination

2) Shuttle

- Approximate cost

3) Public transportation

- Approximate cost per visit

4) Foot

5) Taxi/car service

- Approximate total cost per visit (both ways)

- Number of radiation treatments during which at least one other person accompanied patient

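### Trial patients are given a weekly expense diary but the 45 comparators only a survey after radiation, so survey-based costs are at risk of differential recall error of unknown direction and size

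*Combined protocol and SAP*

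**What the plan says.** For trial patients, Section 7 (Study Calendar, footnote 4) and Section 8.4 both provide a diary during radiation and both give its purpose. Footnote 4 reads: "Health Care Expense Diary should be provided to the patient each week during RT to assist in recall for the Health Care Expense Survey". Section 8.4 reads: "Patients will be given a diary with question domains to be filled out weekly during radiation therapy in order to help improve recall". Footnote 8 then links the two instruments: "Health Care Expense Survey should be completed using the Health Care Expense Diary worksheet (Appendix III) during the 2-8 week window". Appendix III adds that the survey questions come with the diary, so its holder knows in advance what will be asked.

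For the comparison group, Section 8.4 says that "this survey will be administered to an additional 45 patients undergoing standard of care hypofractionated radiation". Footnote 12 says they "should be provided this survey at 2-8 weeks post standard of care hypofractionated radiation". Footnote 13, repeated in Section 12.1, ties consent to the survey: "Patients who volunteer to complete the Health Care Expense Survey must be provided with the Informed Consent Letter prior to completing the questionnaire". On comparability, Section 8.4 says: "This comparison cohort will be case-matched for distance to treatment facility and employment status". Section 2.6 describes the cost comparators as "45 de-identified patients that were treated with a standard hypofractionated regimen of 19 treatments".

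Section 1.2.4 makes direct and indirect patient cost a secondary objective. Section 9.2.4 converts treatment time, travel and lost productivity into costs that enter the incremental cost-effectiveness ratio.

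**The concern.** The protocol supplies the diary because it expects recall to need help, and then specifies that help for only one of the two groups it compares. The group with no specified aid also has the longer course to report on. If accuracy differs between groups, the difference in reported cost mixes a treatment effect with a measurement effect.

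Matching on distance and employment does not address this. Nor does regression on baseline characteristics, because under the written procedure the collection method has no variation within group. The sensitivity analyses in Section 9.2.4 vary parameters within their statistical uncertainty (simulation, and one-way ranges over 95% confidence intervals). They do not allow for a systematic reporting error in one group. At stake is the survey-based part of the economic objective; the primary cosmetic endpoint is not involved.

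**Working it through.** The protocol gives no calculation for the 45 comparators and no recall error, so there is no stated figure to reproduce. The check is a comparison of the text, followed by illustrations.

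**1. What each group is specified to receive**

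| | Trial patients | 45 comparators |
|---|---|---|
| Diary during radiation | Yes, weekly (footnote 4, Section 8.4) | None specified |
| Survey questions seen in advance | Yes (Appendix III) | None specified |
| First specified contact | Before radiation | Consent letter, before the survey |
| Survey | 2-8 weeks after radiation, using the diary | 2-8 weeks after radiation |
| Treatments | 9 | 19 (Section 2.6) |

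I take the 45 patients in Section 2.6 and the 45 in Section 8.4 to be the same group.

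**2. Span to be recalled**

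Assume five fractions a week from a Monday start. Nine fractions span 9 + 2 = 11 calendar days (the Study Summary gives 11-14). Nineteen span 19 + 6 = 25. Adding 14 to 56 days to the survey:

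- Trial patients: 11 + 14 = 25 to 11 + 56 = 67 days from the start, with weekly diary entries.
- Comparators: 25 + 14 = 39 to 25 + 56 = 81 days, with no specified aid.

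**3. Which survey items depend on recall (Appendix II)**

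- Cumulative: days unable to work, part-time days and reduced hours, accompanied treatments, lodging, child care, lost wages. These are the most exposed.
- Per visit: hours per treatment, distance, parking or fare. The patient reports a typical value and the number of visits comes from the regimen, so exposure is smaller.
- Direct medical costs: taken from institutional financial or claims data (Sections 2.6 and 8.4), so not exposed.

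**4. Illustration of sensitivity**

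Let r be the ratio of reported to true value in comparators (assumed), with trial patients reporting accurately (also assumed). If k is the true ratio of trial to comparator totals, the relative shift in the difference is (r - 1)/(1 - k).

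*Quantity proportional to visits.* An example is accompanied treatments, if the share accompanied is equal. Here k = 9/19 = 0.474 and the observed difference is 19r - 9, against a true 10.

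| r | Observed difference | Shift |
|---|---|---|
| 0.7 | 4.3 | -57% |
| 0.8 | 6.2 | -38% |
| 0.9 | 8.1 | -19% |
| 1.0 | 10.0 | 0 |
| 1.1 | 11.9 | +19% |
| 1.2 | 13.8 | +38% |
| 1.3 | 15.7 | +57% |

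The sign reverses only if r falls below 0.474.

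*Quantity accruing evenly over the lost-work period.* That period runs from the first day of radiation to 40 days after it: 11 + 40 = 51 days against 25 + 40 = 65. Then k = 51/65 = 0.785 and the true difference is 14. At r = 0.9 the observed difference is 58.5 - 51 = 7.5 (-46%). At r = 1.1 it is 71.5 - 51 = 20.5 (+46%). The sign reverses below r = 0.785.

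The second case is an assumption about how lost work accrues, not a finding. It shows only that the closer the true totals, the more a given reporting error matters.

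**5. Diary period**

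Footnote 4 and Section 8.4 place the diary during radiation. Appendix III runs it to 6-10 weeks afterwards. The lost-work question stops at 40 days (40/7 = 5.7 weeks), while the survey may be completed from day 14. These periods do not agree with one another in either group.

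**The case against.** The strongest reply is that no passage says comparators go without the diary. Footnote 8 is not limited to trial patients, the survey entry in the calendar carries footnotes 8 and 12 together, and Section 8.4 speaks of patients in general. A reader might infer that comparators answer from memory and that the diary is withheld from them. The documents do not say so; what they support is that no diary is specified for comparators. That narrower point stands, because a diary kept weekly during radiation cannot be supplied by a procedure whose only specified contact comes at the survey.

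A reader might also infer that the cost difference is biased, or that comparators under-report. Nothing in the documents gives a direction or size. Under-reporting would shrink the apparent saving and work against the protocol's hypothesis; over-reporting would inflate it.

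Three further replies have force:

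- The 9-versus-19 arithmetic fits per-visit costs best, and those are the items least exposed to recall. Under it, sign reversal needs under-reporting above 1 - 9/19 = 53%.
- If the diary covers only the radiation weeks, trial patients also recall the period afterwards without it, which narrows the asymmetry.
- The comparison is non-randomised in any case, with comparators who were ineligible for or not interested in the trial. An equal diary would not by itself make the cost-effectiveness ratio sound.

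These limit how much weight the point carries. They do not remove an avoidable difference in measurement between the groups.

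**Conclusion.** The point holds as a risk, not as a demonstrated bias. As written, the method of collecting survey-based costs coincides with treatment group, and nothing in the planned analysis addresses it. Direction and size are unknown. The exposure lies mainly in the cumulative items, is smaller for per-visit items, and is absent for direct costs from financial or claims data.

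The percentage shifts shown are illustrative: they rest on an assumed reporting ratio, accurate reporting by trial patients, and assumed true totals. They should not be read as an estimate of the error in this trial, nor as evidence that the expected saving would disappear. The point deserves correction because the remedy is cheap and a named secondary objective depends on the data. It has no bearing on the primary endpoint or on safety.

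**What to change.** Amend Study Calendar footnotes 12 and 13 and Section 8.4 so that comparators receive the same diary, with the survey questions, from their first week of radiation, and receive the consent letter at that point. Make Section 12.1 consistent. State one diary period in footnote 4, Section 8.4 and Appendix III, and align it with the 40-day lost-work question and the survey timing in both groups. If comparators already receive the diary in practice, the protocol should say so.

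Record diary use for every survey. For comparators surveyed without one, add to Section 9.2.4 a sensitivity analysis on the cumulative items over a stated range of reporting error in both directions, and report the limitation. This part is feasible even if comparator data collection is complete.

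The cost is printed forms, an amended consent procedure, and identifying and matching comparators at the start of radiation instead of after its end. They already attend for treatment, so no visits are added. Earlier approach and weekly diaries may slightly reduce participation.
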